The protocol, informed consent form(s), recruitment materials, and all participant materials will be submitted to the Institutional Review Board (IRB) for review and approval. Approval of both the protocol and the consent form must be obtained before any participant is enrolled. Any amendment to the protocol will require review and approval by the IRB before the changes are implemented to the study. In addition, all changes to the consent form will be IRB-approved; a determination will be made regarding whether a new consent needs to be obtained from participants who provided consent, using a previously approved consent form.

1 PROTOCOL SUMMARY

1.1 SYNOPSIS

Title: Pulsed Electromagnetic Field (PEMF) Therapy in Thumb CMC Arthritis

Study Description: Thumb carpometacarpal (CMC) osteoarthritis (OA) is a common source of

hand pain with limited non-operative treatment options. Pulsed

electromagnetic field (PEMF) therapy has been recently shown in studies to be effective in providing sustained pain relief in knee osteoarthritis. This study aimed to assess the efficacy of PEMF therapy for treating thumb

CMC OA pain.

Objectives: To determine the effects of PEMF therapy on thumb CMC joint pain

Endpoints: Numeric Pain Rating Scale (NPRS) at 4 weeks

Study Population: 60 participants over age 18 with diagnosis of thumb CMC OA

Phase: N/A

Description of Single outpatient orthopedic hand clinic

Sites/Facilities Enrolling

Participants:

[figure not shown]
Description of Study

PEMF device for 8 hours nightly for 4 weeks

Intervention:

Study Duration: 36 months **Participant Duration:** 6 weeks

1.2 SCHEMA

1.3 SCHEDULE OF ACTIVITIES (SOA)

Procedures	Screening Day -7 to -1	Enrollment/Baseline Visit 1, Day 0	Questionnaire #1 Day 7	Questionnaire #2 Day 14	Questionnaire #3 Day 21	Questionnaire #4 Day 28	Questionnaire #5 Day 35	Questionnaire #6 End of Study, Day 42
Informed consent	Х							
Demographics	Х							
Medical history	X							
Randomization	Χ							
Physical Examination		Χ						
Administer study intervention		Χ	Χ	Χ	Χ	Χ		
Patient-reported outcome measures		х	х	Х	Х	х	Х	Х
Adverse event reporting			Χ	Χ	Х	Χ	Χ	Х

2 INTRODUCTION

2.1 STUDY RATIONALE

Recalcitrant pain from thumb carpometacarpal (CMC) osteoarthritis (OA) contributes significantly to failed non-operative management in 15-30% of patients. High-frequency pulsed electromagnetic field (PEMF) therapy is a novel treatment option that has recently demonstrated pain reduction and improved function in knee OA after four weeks of daily, home-based, overnight treatment sessions. This therapy is a safe, pain-free, non-pharmacologic solution that has the potential to solve the limitations of current conservative standard of care with CMC OA. No studies exist to date that have assessed whether PEMF therapy is effective for CMC OA, whether pain reduction effect persists beyond the treatment period, or if disease-modifying physiological changes occur as a result from treatment. To address this problem, we aim to provide high-quality evidence for the use of high-frequency PEMF therapy to treat CMC OA.

2.2 BACKGROUND

Thumb carpometacarpal (CMC) joint osteoarthritis (OA) is a common location of OA in the hand, with an estimated prevalence of 23.5% in patients over the age of 60.⁴ According to 2019 American College of Rheumatology (ACR) guidelines for management of OA, current recommendations for standard of care for CMC OA include splinting, hand therapy exercises, oral non-steroidal anti-inflammatory drugs (NSAIDs), and corticosteroid injections. However, 15-30% of patients proceed to operative management within 1-2 years after starting non-operative management, most commonly due to continued pain rather than functional limitations.^{1,2}

The current standard of non-operative care has substantial limitations. Splinting, although effective, limits daily hand function,⁵ and has a known low therapy adherence. Hand therapy reimbursement in the United States is limited and home exercise adherence is poor. Long term use of oral NSAIDs can lead

to kidney and gastrointestinal damage. Corticosteroid injections provide only temporary relief in a subset of patients, and repeat injections may lead to greater cartilage volume loss. In addition, there are limited options for patients who have pain recalcitrant to these non-operative management options.

High-frequency pulsed electromagnetic field (PEMF) therapy is an innovative treatment option that has the potential to address some of the limitations of current standard of care. Currently no studies exist that have assessed whether PEMF therapy is effective for CMC OA. PEMF wearable devices emit non-painful low-power pulsed shortwaves and have no reported adverse effects. Pain reduction with this therapy has been shown to persist beyond the treatment period for knee OA.³ While pulsed shortwave therapy was previously performed in an outpatient setting, these devices allow for home use with more frequent treatment sessions. These proposed benefits will help address barriers to patient adherence with current treatment options for CMC OA and provide another nonpharmacologic modality for patients with recalcitrant CMC OA pain.

2.3 RISK/BENEFIT ASSESSMENT

2.3.1 KNOWN POTENTIAL RISKS

There are no adverse effects reported in previously published studies. 3,7,8

2.3.2 KNOWN POTENTIAL BENEFITS

Prior studies on PEMF therapy have largely focused on its application to knee OA. In a recent metaanalysis by Wu et al., there was significant pain reduction for patients with knee OA, though studies varied in the frequency and intensity of the pulsed electromagnetic field, as well as the frequency and duration of therapy. To date, there is only one pilot study on the effects of PEMF therapy on hand OA in 50 patients. Kanat et al. demonstrated that low-frequency (25 Hz) PEMF therapy when applied for 20 minutes per day for 10 days, combined with active range of motion and strengthening exercises, improved pain and Short Form-36 social function and general health outcome measures when compared to sham PEMF therapy with the same exercises.

2.3.3 ASSESSMENT OF POTENTIAL RISKS AND BENEFITS

With no known potential adverse effects and a known potential benefit of pain reduction, more studies are needed that demonstrate efficacy of PEMF therapy in setting of an overall promising safety profile.

3 OBJECTIVES AND ENDPOINTS

OBJECTIVES	ENDPOINTS	JUSTIFICATION FOR ENDPOINTS
Primary		
Determine the effects of PEMF therapy on thumb CMC joint pain	Outcome measures at 4 weeks: Numeric Pain Rating Scale (NPRS) Patient Rated Wrist/Hand Evaluation (PRWHE) Single Assessment Numeric Evaluation (SANE)	Previous studies have shown pain reduction after 4 weeks of PEMF therapy.

OBJECTIVES	ENDPOINTS	JUSTIFICATION FOR ENDPOINTS
Secondary		
Determine if sustained effects persist beyond the treatment period	Outcome measures at 6 weeks: Numeric Pain Rating Scale (NPRS) Patient Rated Wrist/Hand Evaluation (PRWHE) Single Assessment Numeric Evaluation (SANE)	Several studies have reported pain reduction sustained for weeks to months past treatment cessation.

4 STUDY DESIGN

4.1 OVERALL DESIGN

This study is a single-center, double-blind, randomized, controlled trial. Participants will be randomly assigned to either the experimental group or control group in a block size of 10 with an allocation ratio of 1:1.

4.2 SCIENTIFIC RATIONALE FOR STUDY DESIGN

The study design is based on the methodology of a published randomized controlled trial on PEMF therapy for knee OA.³

4.3 JUSTIFICATION FOR DOSE

The dosing is based on the methodology of a published randomized controlled trial on PEMF therapy for knee OA.³

4.4 END OF STUDY DEFINITION

A participant is considered to have completed the study if he or she has completed all phases of the study including the last visit or the last scheduled procedure shown in the Schedule of Activities (SoA), Section 1.3. The end of the study is defined as completion of the last visit or procedure shown in the SoA in the trial globally.

5 STUDY POPULATION

5.1 INCLUSION CRITERIA

In order to be eligible to participate in this study, an individual must meet all of the following criteria:

1. Provision of signed and dated informed consent form

- 2. Stated willingness to comply with all study procedures and availability for the duration of the study
- 3. Over the age of 18
- 4. Clinically and/or radiographically diagnosed thumb CMC OA
- 5. Reported average pain intensity during activities of daily living between "3" and "8" on the Numeric Pain Rating Scale (NPRS)

5.2 EXCLUSION CRITERIA

An individual who meets any of the following criteria will be excluded from participation in this study:

- 1. Pregnancy
- 2. Inability to consent
- 3. Current infection of the upper extremity
- 4. Prior fracture, severe hand injury, tenosynovitis, complex regional pain syndrome and/or Dupuytren's disease affecting the thumb
- 5. History of surgical or procedural intervention for CMC OA at the site of interest
- 6. Hand, wrist, heart, or brain implants

5.3 LIFESTYLE CONSIDERATIONS

Not applicable.

5.4 SCREEN FAILURES

Screen failures are defined as participants who consent to participate in the clinical trial but are not subsequently randomly assigned to the study intervention or entered in the study. A minimal set of screen failure information is required to ensure transparent reporting of screen failure participants, to meet the Consolidated Standards of Reporting Trials (CONSORT) publishing requirements and to respond to queries from regulatory authorities. Minimal information includes demography, screen failure details, eligibility criteria, and any serious adverse event (SAE).

5.5 STRATEGIES FOR RECRUITMENT AND RETENTION

Members of the study team will review the clinic schedule through EPIC each week to identify eligible patients and recruitment will be through phone calls of patients with diagnosis of thumb CMC OA or at the time of their clinic visit. A member of the care team will introduce the study to the patient. If the patient is interested in learning more and/or participating, a member of the research team will provide study-related information and obtain informed consent via written or electronic consent. Recruitment flyers will be posted at the Stanford Orthopaedic Clinic with study information. Patients who may qualify will have the option to reach out to the study coordinator if they are interested in participating. A member of the research team will provide study-related information and obtain informed consent via written or electronic consent If a patient consents to participate, the patient will be randomized into either the study group or the control group. Recruitment will involve 60 participants total.

6 STUDY INTERVENTION

6.1 STUDY INTERVENTION(S) ADMINISTRATION

6.1.1 STUDY INTERVENTION DESCRIPTION

The experimental group will receive a PEMF device that has received 510(k) clearance by the United States Food and Drug Administration (FDA) (ActiPatch, BioElectronics Corporation, Frederick, MD), modified by the device manufacturer to have a shorter antenna size of 4.5 cm diameter while otherwise maintaining all other device parameters within its FDA clearance. The device emits pulsed electromagnetic waves in shortwave frequencies (27.12 MHz) at a rate of 1000 Hz with average spatial power density of $4.4~\mu Watts/cm^2$.

The control group will receive a sham device that is identical in appearance but does not emit any electromagnetic wave.

6.1.2 DOSING AND ADMINISTRATION

Both groups will be instructed to wear the device nightly for four weeks by fixing the loop of the device on their thenar eminence with medical-grade tape and place the center of the loop around the area of greatest pain.

6.2 PREPARATION/HANDLING/STORAGE/ACCOUNTABILITY

6.2.1 ACQUISITION AND ACCOUNTABILITY

The PEMF and sham devices will be provided to the investigator by the device manufacturer (BioElectronics Corporation, Frederick, MD), consecutively numbered by the device manufacturer based on a randomization schedule with a block size of 10 and allocation ratio of 1:1.

6.2.2 FORMULATION, APPEARANCE, PACKAGING, AND LABELING

The PEMF and sham devices appear identical except for a label with the device number.

6.2.3 PRODUCT STORAGE AND STABILITY

Devices will be stored in a secure location.

6.2.4 PREPARATION

Devices will be tested prior to being provided to the study participant that it can be powered on/off.

6.3 MEASURES TO MINIMIZE BIAS: RANDOMIZATION AND BLINDING

To ensure the research study personnel and participants were blinded to the group allocation prior to study enrollment, the PEMF and sham devices will be provided, tested by, and consecutively numbered by the device manufacturer.

6.4 STUDY INTERVENTION COMPLIANCE

Participants will be provided a daily log to record number of hours of device use and will report this as an average in weekly questionnaires.

6.5 CONCOMITANT THERAPY

Participants will report average over-the-counter medication and thumb CMC splint use in weekly questionnaires.

6.5.1 RESCUE MEDICINE

Not applicable.

STUDY INTERVENTION DISCONTINUATION AND PARTICIPANT DISCONTINUATION/WITHDRAWAL

7.1 DISCONTINUATION OF STUDY INTERVENTION

Discontinuation of device use does not mean discontinuation from the study, and remaining study procedures should be completed as indicated by the study protocol. If a clinically significant finding is identified (including, but not limited to changes from baseline) after enrollment, the investigator or qualified designee will determine if any change in participant management is needed. Any new clinically relevant finding will be reported as an adverse event (AE).

7.2 PARTICIPANT DISCONTINUATION/WITHDRAWAL FROM THE STUDY

Participants are free to withdraw from participation in the study at any time upon request.

An investigator may discontinue or withdraw a participant from the study for the following reasons:

- Pregnancy
- Significant study intervention non-compliance
- If any clinical adverse event (AE), laboratory abnormality, or other medical condition or situation occurs such that continued participation in the study would not be in the best interest of the participant
- Disease progression which requires discontinuation of the study intervention
- If the participant meets an exclusion criterion (either newly developed or not previously recognized) that precludes further study participation

Subjects who sign the informed consent form, and are randomized and receive the study intervention, and subsequently withdraw, or are withdrawn or discontinued from the study, will not be replaced.

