9.4.2 ANALYSIS OF THE PRIMARY EFFICACY ENDPOINT(S)

NPRS at 4 weeks will be analyzed with Mann-Whitney U-test for between-group comparison. Participants with missing data or lost to follow-up will be excluded from analysis.

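### Section 7.2 allows withdrawal from the study for device non-compliance or progression, so Day 28 pain scores that could still be collected may be lost

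*Combined protocol and SAP*

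**What the plan says.** Section 7.1 sets the default: "Discontinuation of device use does not mean discontinuation from the study, and remaining study procedures should be completed as indicated by the study protocol". Section 7.2 then gives the investigator a discretionary power: "An investigator may discontinue or withdraw a participant from the study for the following reasons". Two of the five listed reasons concern use of the device: "Significant study intervention non-compliance", for which no threshold in hours or nights is given, and "Disease progression which requires discontinuation of the study intervention". Participants who received the intervention and later withdraw, "or are withdrawn or discontinued from the study, will not be replaced".

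The Schedule of Activities (1.3) shows one visit, on Day 0. Days 7 to 42 are weekly questionnaires, and 8.1 confirms that efficacy is patient-reported each week. Under 6.4 participants log device hours and "will report this as an average in weekly questionnaires". The primary endpoint is NPRS at 4 weeks (9.1), collected at Day 28. Section 9.3 declares an intention-to-treat set of all randomized participants, while 9.4.2 says: "Participants with missing data or lost to follow-up will be excluded from analysis". The design is a "single-center, double-blind, randomized, controlled trial" (4.1).

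**The concern.** Sections 7.1 and 7.2 can be read together as a rule and an exception. The difficulty is what the exception covers. The progression reason is defined by stopping the device, which is the event that 7.1 says should not end participation. The non-compliance reason is about device use alone. Neither makes a self-reported pain score impossible to collect. Device hours come in weekly, so non-compliance can become visible on Day 7, 14 or 21, and the power can be used before the primary endpoint is measured.

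Once it is used, a decision taken after randomization becomes an exclusion from the primary analysis. Non-compliance and progression both plausibly depend on pain, so those lost may differ from those who stay. If the device works and people with much pain are withdrawn, more are lost from sham and the remaining sham group looks better than it should. If people stop wearing the device because they feel better, more are lost from the active arm and the remaining active group looks worse. Both routes pull the estimated benefit towards zero.

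**Working it through.** **Does the loss follow from the text?** Stopping the device leaves the participant in the study (7.1). The investigator may nevertheless end participation for two device-related reasons (7.2). No section provides for questionnaires afterwards; 7.3 deals with participants who cannot be contacted, not with those the investigator withdraws. There is no replacement (7.2), and missing data mean exclusion (9.4.2). So if the power is used before Day 28, the primary score is lost.

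**Inputs from the plan.** 60 recruited (5.5) at 1:1 (4.1), so 30 per arm; two-sided 0.05 (9.4.1); Mann-Whitney test (9.4.2); effect of 1 on NPRS, power 0.80, 27 per group with 10% withdrawals (9.2).

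**SD implied by 9.2.** None is stated. Reading the effect as 1 point, n per arm = 2(1.960 + 0.842)² × SD² / 1². With SD 1.22 this is 23.4, so 24, and 24/0.90 = 26.7, so 27, matching 9.2. Solving a t-test with 25 per arm gives SD 1.24, used below. A standardized effect of 1 would need only 18 to 20 per arm after inflation, which does not match.

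**Assumptions not in the plan.** Mean NPRS 5; SD 1.24, or 2.0 as an alternative; correlation of earlier with Day 28 pain 0.5 to 0.9; scores rounded and kept within 0 to 10. Each participant with earlier pain of at least 6 (SD 1.24) or at least 7 (SD 2.0) is withdrawn with probability 0.25, whatever the arm. Simulation used 6,000 trials per case.

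**No true effect.** Rejection is 0.046 to 0.051 and bias is within 0.01.

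**True 1-point benefit, high-pain participants withdrawn.**

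| SD | Correlation | Estimate, full data → after withdrawal | Power, full data → after withdrawal | Power, same number lost at random |
|---|---|---|---|---|
| 1.24 | 0.5 | 0.999 → 0.970 | 0.828 → 0.787 | 0.803 |
| 1.24 | 0.7 | 0.997 → 0.954 | 0.829 → 0.783 | 0.806 |
| 1.24 | 0.9 | 0.999 → 0.944 | 0.835 → 0.785 | 0.814 |
| 2.0 | 0.5 | 0.983 → 0.954 | 0.445 → 0.416 | 0.422 |
| 2.0 | 0.7 | 0.993 → 0.945 | 0.453 → 0.415 | 0.435 |
| 2.0 | 0.9 | 0.976 → 0.918 | 0.440 → 0.395 | 0.425 |

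Mean numbers lost, active v sham, are 0.86 v 2.58 (SD 1.24) and 0.80 v 1.69 (SD 2.0). Attenuation runs from (0.999 − 0.970)/0.999 = 3% to (0.976 − 0.918)/0.976 = 6%. Power falls by 3 to 5 points, about 2 of them from smaller numbers alone.

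**True 1-point benefit, low-pain participants withdrawn** (earlier pain at most 3, correlation 0.7). SD 1.24: estimate 0.999 → 0.954, power 0.831 → 0.776, lost 2.58 v 0.86. SD 2.0: estimate 0.985 → 0.950, power 0.452 → 0.400, lost 3.00 v 1.73. Attenuation is about 4% and power falls by 5 to 6 points.

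**Lower withdrawal probability** (high pain, SD 1.24, correlation 0.7). At 10%: 0.998 → 0.982, power 0.832 → 0.813. At 5%: 1.004 → 0.995, power 0.835 → 0.826.

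**Chance imbalance in a single trial.** If three of 60 are withdrawn blind to arm and there is no effect, all three fall in one arm with probability 2 × C(30,3)/C(60,3) = 2 × 4,060/34,220 = 0.237. If those three come from the ten highest earlier scores in that arm, the between-arm difference shifts by 0.10 (SD 1.24) or 0.16 (SD 2.0) points at correlation 0.7, and by 0.08 to 0.23 over correlations 0.5 to 1.0. A simple check agrees: shift = share lost × gap between lost and retained, so 3/30 × 1 point = 0.10.

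**The case against.** The strongest reply is that 7.1 already protects the data and 7.2 is only a reserve power. The plan describes no compliance review and no trigger for using it. Progression that requires stopping the device within 28 days also looks rare in a chronic condition, with a device for which 2.2 and 2.3.1 report no adverse effects. This stands as a reason to expect few cases. It gives no reason to keep two grounds that discard data the trial could still collect.

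The 25% rate has no support in the plan and drives the result. At SD 1.24 it removes 2.58 of 30 sham participants, about 9%, close to the whole 10% allowance for withdrawals. The model also withdraws people for pain, so its link to non-compliance is assumed. This stands: the 3 to 6% attenuation is an upper scenario.

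Withdrawals are budgeted, since 60 are recruited against a calculated 54. The modelled losses of 2.5 to 4.7 leave at least 55, above the roughly 48 to 50 evaluable that 9.2 implies. That answers the loss of numbers but not selective loss.

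The 3 v 0 figures show chance imbalance that can go either way; they are not bias. That is correct, and they should be read so.

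Finally, the harm passes through the exclusion rule in 9.4.2, which this change leaves in place for voluntary dropout and loss to follow-up. True, but no analysis rule recovers scores that were never collected.

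**Conclusion.** The concern holds and is minor. What the text permits is clear: two device-related reasons can end follow-up before Day 28, and the affected participants then leave the primary analysis. The size is uncertain because the plan gives no frequency. With withdrawal blind to arm, no type I inflation is expected. A true 1-point benefit would be attenuated by about 1 to 2% at a 5 to 10% withdrawal probability (SD 1.24, correlation 0.7), and by 3 to 6% at 25% across the SDs and correlations assumed. All these shifts are small against the minimal important difference of 2 in 9.4.1. The case for change rests on the loss being avoidable, since the questionnaires are already scheduled.

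**What to change.** In 7.2, make device non-compliance, and progression that requires stopping the device, reasons for stopping the device only. State that these participants are still sent every remaining questionnaire through Day 42, including the Day 28 NPRS, unless they withdraw consent or continued participation is not in their best interest. Leave the pregnancy, adverse event/best-interest and exclusion-criterion grounds as they are. Record the date and reason for stopping the device separately from the date and reason for leaving the study.

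The cost is a short protocol amendment and one extra case report form field, with no added visits, questionnaires or participants. The downside is some dilution of the estimate by people not using the device, which the intention-to-treat set in 9.3 already accepts.

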7.3 LOST TO FOLLOW-UP

A participant will be considered lost to follow-up if he or she fails to complete subsequent weekly questionnaires and is unable to be contacted by the study site staff.

The following actions must be taken if a participant fails to return to the clinic for a required study visit:

- The site will attempt to contact the participant and counsel the participant on the importance of completing the assigned questionnaires weekly and ascertain if the participant wishes to and/or should continue in the study.
- Before a participant is deemed lost to follow-up, the investigator or designee will make every effort to regain contact with the participant.
- Should the participant continue to be unreachable, he or she will be considered to have withdrawn from the study with a primary reason of lost to follow-up.

